7.2.2 Medications Prohibited

- Live, attenuated vaccines (e.g., FluMist®) are prohibited within 4 weeks prior to initiation of study treatment, during treatment with atezolizumab, and for 5 months after the last dose of atezolizumab.
- Systemic immunostimulatory agents (including, but not limited to, interferons and interleukin 2) are prohibited within 12 weeks or five half-lives of the drug, whichever is longer, prior to initiation of study treatment and during study treatment because these agents could potentially increase the risk for autoimmune conditions when given in combination with atezolizumab.
- Systemic immunosuppressive medications (including, but not limited to, cyclophosphamide,

Columbia University Irving Medical Center
Herbert Irving Comprehensive Cancer Center
AAAS4165_Version Date: 07/07/2021

azathioprine, methotrexate, and thalidomide) are prohibited during study treatment because these agents could potentially alter the efficacy and safety of atezolizumab.

7.4 Duration of Follow Up

Participants will be followed for up to 5 years after completion or removal from study treatment or until death, whichever occurs first. Participants removed from study treatment for unacceptable adverse events will be followed until resolution or stabilization of the adverse event. A post-study follow-up contact via phone by site staff will be conducted every 3 months during years 1 and 2, then every 6 months thereafter to obtain information on any new anti-cancer therapy received and survival status.

A participant will be considered lost to follow-up if he or she fails to return for 3 scheduled visits and is unable to be contacted by the study site staff.

The following actions must be taken if a participant fails to return to the clinic for a required study visit:

- The site will attempt to contact the participant and reschedule the missed visit within 2 weeks, counsel the participant on the importance of maintaining the assigned visit schedule, and ascertain if the participant wishes to and/or should continue in the study.
- Before a participant is deemed lost to follow-up, the Investigator or designee will make every effort to regain contact with the participant (where possible, at least 3 telephone attempts). These contact attempts should be documented in the participant's medical record or study file.
- Should the participant continue to be unreachable, he or she will be considered to have withdrawn from the study with a primary reason of lost to follow-up.

7.5 Criteria for Removal from Study

Participants will be removed from study when any of the criteria listed in Section 7.4 applies. The reason for study removal and the date the patient was removed will be documented in the Case Report Form.

8. ADVERSE EVENTS AND DOSING DELAYS/MODIFICATIONS

8.1 General guidelines on dose delays and/or modifications

Dose Modifications –

Dose reductions during the DLT period are not allowed, unless a DLT is confirmed. If the subject experiences a DLT, they should be removed from the study unless the subject is deriving clinical benefit, as determined by the Investigator in consultation with the Principal Investigator.

Dose modifications will be allowed if subject does not tolerate therapy after the DLT period, as described (Section 8.2).

Dose Interruptions –

Dose interruptions are allowed during the DLT period as long subjects receive 90% of the scheduled doses. Doses held due to toxicity will not be replaced within the same cycle. If a drug is held due to toxicity, the other drug(s) may be administered as scheduled. If hydroxychloroquine and/or cobimetinib is held for longer than 28 days, all treatments should be permanently discontinued and the patient removed from study, unless the subject is deriving clinical benefit as determined by the Investigator in consultation with the Principal Investigator. If atezolizumab is held for longer than 105 days, atezolizumab should be permanently discontinued; however, hydroxychloroquine and cobimetinib may be continued.

8.2 Drug-specific dose delays/modifications

8.2.1 Dose modifications: Atezolizumab

There will be no dose modifications for atezolizumab in this study. Atezolizumab treatment may be temporarily suspended in patients experiencing toxicity considered to be related to study treatment. If corticosteroids are initiated for treatment of the toxicity, they must be tapered over ≥ 1 month to ≤ 10 mg/day oral prednisone or equivalent before atezolizumab can be resumed. If atezolizumab is withheld for >105 days, the patient will be discontinued from atezolizumab. However, atezolizumab may be withheld for >105 days to allow for patients to taper off corticosteroids prior to resuming treatment. Atezolizumab can be resumed after being withheld for >105 days if the Principal Investigator agrees that the patient is likely to derive clinical benefit. Toxicities associated or possibly associated with atezolizumab treatment should be managed according to standard medical practice. Additional tests, such as autoimmune serology or biopsies, should be used to evaluate for a possible immunogenic etiology. Although most immune-related adverse events observed with immunomodulatory agents have been mild and self-limiting, such events should be recognized early and treated promptly to avoid potential major complications. Discontinuation of atezolizumab may not have an immediate therapeutic effect, and in severe cases, immune-related toxicities may require acute management with topical corticosteroids, systemic corticosteroids, or other immunosuppressive agents. The investigator should consider the benefit-risk balance a given patient may be experiencing prior to further administration of atezolizumab. In patients who have met the criteria for permanent discontinuation, resumption of atezolizumab may be considered if the patient is deriving benefit and has fully recovered from the

immune related event. Patients can be re-challenged with atezolizumab only after approval has been documented by both, the Investigator (or an appropriate delegate) and the Principal Investigator. Please refer to Appendix 1 for management of atezolizumab-related adverse events.

8.2.2 Dose modifications: Cobimetinib

Allowable dose modifications for Cobimetinib are described in Table 6. Cobimetinib treatment may be temporarily suspended in patients who experience toxicity considered to be related to study treatment. After dose reduction, the dose of cobimetinib may be escalated by a maximum of one dose level (20 mg) increments at the Investigator's discretion in consultation with the Principal Investigator, provided there are no safety concerns. If cobimetinib has been withheld for >28 days because of toxicity, the patient should be discontinued from cobimetinib, unless resumption of treatment is approved following Investigator discussion with the Principal Investigator. The Principal Investigator should be consulted for any major surgery (e.g., involving a body cavity), and cobimetinib should generally be withheld for 12 hours prior to the procedure and for 2 weeks thereafter.

Table 6. Cobimetinib dose modifications

| Dose Level | Cobimetinib (mg) TDD |
|-------------------|-----------------------------|
| -1 | 40mg (orally in AM) |
| -2 | 20mg (orally in AM) |

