4. STUDY DESIGN

4.1 General Design

4.1.1 Phase 1

The objective of this study is to determine the maximum tolerated dose (MTD) of the combination of cobimetinib, atezolizumab, and hydroxychloroquine. We will evaluate three dose combinations. Patients will be treated with combination therapy at the designated dose levels depicted in Table 1, based on a 28 day cycle (Section 7.3). The MTD is defined as the dose associated with a target probability of dose limiting toxicity of 0.30. The primary endpoint is DLT in the first cycle of treatment.

Columbia University Irving Medical Center
Herbert Irving Comprehensive Cancer Center
AAAS4165_Version Date: 07/07/2021

Given that cobimetinib is approved at a dose of 60 mg orally daily and hydroxychloroquine was well tolerated at 600 mg orally twice daily, we feel that the combination will be well tolerated (Wolpin et al., 2014). Cobimetinib and atezolizumab were tested in advanced colorectal cancer in IMblaze370, a large randomized phase 3 clinical trial (Eng et al., 2019) with proportion of patients experiencing grade 3 and over adverse events similar to those who received the FDA approved Regorafenib. Subjects will receive cobimetinib in cohort 1 and 2 at a lower dose (40mg oral daily) compared to that tested in IMblaze370 (60mg oral daily). Given that, other than ocular and hepatic toxicity, hydroxychloroquine has little to no overlapping adverse events with cobimetinib and atezolizumab, we do not anticipate significant toxicities with this combination at the doses being tested. Ocular toxicities with hydroxychloroquine are observed at high cumulative doses and will be monitored by required scheduled ophthalmological evaluations throughout the study period. We will initiate Phase 1 at dose level 1 using a combined 3+4 and time-to-event continual reassessment method (TITE-CRM). Table 1. Cohort dose levels.

| Patient No. | Dose Level | Hydroxychloroquine (mg) (oral; 1200mg/day; Days 1-28) | Cobimetinib (mg) (oral; 40-60mg/day; Days 1-21) | Atezolizumab (mg) (IV; 840mg every two weeks) |
|------------------|------------|---|---|---|
| 1, 2, 3 | 1 | 600mg twice per day | 40mg | |
| 4, 5, 6 | 2 | 600mg twice per day | 40mg | 840mg |
| 7, 8, 9 10-18 | 3 | 600mg twice per day TITE-CRM | 60mg | 840mg |

Phase I Statistical Considerations

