7.1.2 Cobimetinib

In this study, cobimetinib will be administered orally once daily (morning) on Days 1-21 of each 28-day cycle. Cobimetinib will be supplied as 20-mg, film-coated tablets packaged in blister packs (21 tablets per pack; 3 packs per box) for oral administration. Cobimetinib should be taken approximately the same time in the morning, and no later than 4 hours after the scheduled time. Cobimetinib may be taken with or without a meal. Cobimetinib should be swallowed whole with a glass of water and should not be chewed, cut, or crushed. If a dose of cobimetinib is missed (i.e., not taken within 12 hours after the scheduled dosing time), the patient should resume dosing with the next scheduled dose. Missed or vomited doses will not be made up. For information on the formulation and handling of cobimetinib, see the pharmacy manual and the Cobimetinib Investigator's Brochure.

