8.2.3 Dose modifications: Hydroxychloroquine

Allowable dose modifications for Hydroxychloroquine are described in Table 7.

The 4-aminoquinoline compounds are very rapidly and completely absorbed after ingestion. In accidental overdosage, or rarely with lower doses in hypersensitive patients, toxic symptoms may occur within 30 minutes. The symptoms of overdosage may include headache, drowsiness, visual disturbances, cardiovascular collapse, convulsions, hypokalemia, rhythm and conduction disorders, including QT prolongation, torsades de pointes, ventricular tachycardia and ventricular fibrillation, followed by sudden, potentially fatal respiratory and cardiac arrest. Treatment is symptomatic and must be prompt. Immediate gastric lavage until the stomach is completely emptied is indicated. After lavage, activated charcoal is introduced by the stomach tube within 30 minutes of ingestion of the drug may inhibit further intestinal absorption. To be effective, the dose of activated charcoal should be at least five times the estimated dose of hydroxychloroquine ingested.

Consideration should be given to administering diazepam parenterally since studies suggest that it may be beneficial in reversing chloroquine and hydroxychloroquine cardiotoxicity.

Respiratory support and shock management should be instituted as necessary.

Exchange transfusions are used to reduce the level of 4-aminoquinoline drug in the blood.

Columbia University Irving Medical Center
Herbert Irving Comprehensive Cancer Center
AAAS4165_Version Date: 07/07/2021

A patient who survives the acute phase and is asymptomatic should be closely observed for at least six hours. Fluids may be forced and sufficient ammonium chloride (8 g daily in divided doses for adults) may be administered for a few days to acidify the urine. This will promote urinary excretion in cases of both overdosage and sensitivity. However, caution must be exercised in patients with impaired renal function and/or metabolic acidosis.

Table 7. Hydroxychloroquine dose modification

| Dose Level | Hydroxychloroquine (mg) TDD |
|-------------------|---------------------------------------|
| -1 | 1000mg (400mg AM and 600mg PM orally) |
| -2 | 800mg (400mg BID orally) |
| -3 | 600mg (200mg AM and 400mg PM orally) |

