8.2.4 Dose modifications: Cobimetinib + Hydroxychloroquine with or without Atezolizumab therapy

Dose modification may be made for Cobimetinib and/or Hydroxychloroquine, as necessary, according to the guidelines described (Table 6 and 7), as guided in Appendix 1. If further dose reduction of cobimetinib is indicated after two dose reductions, the patient must discontinue cobimetinib. Similarly, if further dose reduction of hydroxychloroquine is indicated after three dose reductions, the patient must discontinue hydroxychloroquine. Subjects may continue treatment if being administered two of the three study drugs, but may not continue on study with either cobimetinib, hydroxychloroquine, or atezolizumab alone, unless with the approval of the Principal Investigator deeming the subject to be deriving clinical benefit.

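### Table 6's cobimetinib reduction ladder fits only a 60 mg start; for patients who start at 40 mg, level -1 is the dose they already take

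*Combined protocol and SAP*

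**What the plan says.** Cobimetinib starts at 60 mg only at dose level 3. Section 4.1.1 states: "Subjects will receive cobimetinib in cohort 1 and 2 at a lower dose (40mg oral daily"). The synopsis and Table 1 agree.

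Section 8.2.2 refers all cobimetinib modifications to Table 6. That table has two rows: level -1, "40mg (orally in AM"), and level -2, 20 mg in the morning. It has no row for the starting dose and no split by assigned dose level.

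The size of a level is stated once, in the sentence on going back up: "After dose reduction, the dose of cobimetinib may be escalated by a maximum of one dose level (20 mg) increments".

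Section 8.2.4 covers treatment with or without atezolizumab. It sends cobimetinib and hydroxychloroquine modifications to the tables, "according to the guidelines described (Table 6 and 7), as guided in Appendix 1", and sets the limit: "If further dose reduction of cobimetinib is indicated after two dose reductions, the patient must discontinue cobimetinib".

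On supply, Section 7.1.2 says: "Cobimetinib will be supplied as 20-mg, film-coated tablets packaged in blister packs". The same section forbids cutting or crushing them.

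**The concern.** A reduction ladder should begin below the dose the patient is taking. Table 7 does this for hydroxychloroquine: every patient starts at 1200 mg/day, and level -1 is "1000mg (400mg AM and 600mg PM orally"). Table 6 does it only for a 60 mg start.

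Section 8.2.4 leaves no doubt that Table 6 also governs 40 mg starters. Treatment without atezolizumab is assigned only at dose level 1, which is a 40 mg start. No other section gives these patients a ladder of their own.

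The stake is dosing after serious toxicity. Appendix 1 repeatedly tells the site to resume cobimetinib one level down without naming a starting dose. A site that looks up level -1 for a 40 mg starter finds 40 mg, the dose that preceded the event. Section 17 provides for affiliate sites, so two readings could be in use at once.

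**Working it through.** No power, alpha or sample-size calculation applies. The check compares each starting dose with Table 6 and then looks at where Appendix 1 uses the ladder.

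**Inputs.** Starts: 40, 40 and 60 mg at dose levels 1, 2 and 3 (synopsis; Section 4.1.1, Table 1). Table 6: -1 = 40 mg, -2 = 20 mg. Level size: 20 mg (8.2.2). Limit: two reductions (8.2.4). Tablets: 20 mg, uncut (7.1.2).

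**Ladder.** Dose after k reductions = start - k x 20 mg.

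| Start | k = 1 | Table 6, -1 | k = 2 | Table 6, -2 |
|---|---|---|---|---|
| 60 mg | 60 - 20 = 40 mg | 40 mg (agrees) | 60 - 40 = 20 mg | 20 mg (agrees) |
| 40 mg | 40 - 20 = 20 mg | 40 mg (no reduction) | 40 - 40 = 0 mg | 20 mg |

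Table 6 reproduces the 60 mg ladder exactly. For a 40 mg start, its -1 is the start and its -2 is the first real reduction.

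**Size of one level.** From 60 mg: 20/60 = 33%. From 40 mg: 0/40 = 0% by the label, or 20/40 = 50% by the 20 mg step. For comparison, hydroxychloroquine: 200/1200 = 17%.

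**Reductions available.** A 40 mg starter can go to 20 mg once; the next step is 0 mg. That is one real reduction against the two permitted in 8.2.4. Section 10.1.1 mentions an oral suspension, but 7.1.2 supplies tablets and Table 6 lists nothing below 20 mg.

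**Table 1 levels do not help.** If a level is taken in the Table 1 sense, moving from dose level 2 to dose level 1 removes atezolizumab and leaves cobimetinib at 40 mg.

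**Where the order appears.** A one-level cobimetinib reduction is ordered in these Appendix 1 rows: A1.2 (1), A1.3 (1), A1.4 (1), A1.6 (1), A1.9 (1), A1.10 (4), A1.11 (1), A1.12 first QTc (1) and A1.13 (2). The sum is 13 rows in 9 tables. The two A1.13 rows repeat CPK events already in A1.10, leaving 11 distinct events. The third-QTc row of A1.12 is left out because Section 8.3.1 requires permanent discontinuation at that point.

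**Where cobimetinib is clearly the only drug with an ordered dose reduction.** There are three rows: Grade 2-3 diarrhea or colitis (A1.2), the catch-all for other toxicities (A1.11) and the first QTc above 500 ms (A1.12). In the QTc row, following the label leaves cobimetinib at 40 mg and hydroxychloroquine at 1200 mg/day once treatment resumes. For LVEF decline (A1.10), hydroxychloroquine is reduced as well.

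**How many start at 40 mg.** Summing the Table 2 averages for dose levels 1 and 2: Scenario 1, 11 + 4 = 15; Scenario 2, 6 + 6 = 12; Scenario 3, 2 + 5 = 7, each of 18. These are patients to whom the wrong ladder would apply if they needed a reduction, not patients misdosed.

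**The case against.** The strongest reply is that Appendix 1 never tells a site to set cobimetinib to level -1. Its orders are relative: lower the dose by one level. A patient on 40 mg sits on the 40 mg row, one row down is 20 mg, 8.2.2 sizes a level at 20 mg, and the tablets are 20 mg. This reading serves both starting doses, and the alternative makes a reduction mean no change. It stands as the likely intent. It does not clear the table, because the 20 mg size appears only in the re-escalation sentence and the sensible reading must override Table 6's own label of 20 mg as -2.

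It is also fair that the limit in 8.2.4 is a ceiling, not an entitlement to two steps. By itself it causes no dosing error; it shows that the section was written for a 60 mg start.

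Safeguards narrow the exposure. Section 8.1 bars reductions in the DLT period unless a DLT is confirmed, and otherwise says: "Dose modifications will be allowed if subject does not tolerate therapy after the DLT period". Drug is withheld first in these rows, and resumption generally requires improvement. Principal Investigator review is only a partial backstop: 8.2.2 requires that consultation for re-escalation, not for choosing the reduced dose, and the first-QTc and serious retinopathy rows resume without it.

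A reader might infer that no drug exposure falls in every row where cobimetinib alone has a reduction order. The documents do not support that beyond the three rows named above. In A1.6, atezolizumab is permanently discontinued if the hyperthyroidism is life-threatening. In A1.3, hydroxychloroquine is withheld with no instruction to resume. For Grade 4 CPK, A1.13 reduces only cobimetinib, but A1.10 reduces hydroxychloroquine for the same event.

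**Conclusion.** The point holds as a labelling defect with a safety consequence and should be corrected. Table 6 and the limit in 8.2.4 fit a 60 mg start and misdescribe the 40 mg start of dose levels 1 and 2. The intended first reduction for those patients is probably 20 mg, but the only table of allowable doses labels that as the second step.

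The size is a matter of dose per event: one level is 0% or 50% from 40 mg, depending on the reading, against 33% from 60 mg. The number of patients affected is not in the documents. A reader might apply the 61% interruption-or-modification figure in Section 3.1.4.2 to the 40 mg starters. That figure includes interruptions, comes from 60 mg dosing, and says nothing about how often the table would be misread.

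Nor should a reader infer damage to the dose-finding. A reduction within the DLT period requires a DLT already confirmed, so DLT counting and MTD estimation are unaffected, as are error rates. Phase 2 is exposed only if a 40 mg level is carried forward and the amendment required by Section 4.1.2 leaves the table as it is.

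**What to change.** Key Table 6 to the assigned starting dose:

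- 60 mg start: -1 = 40 mg, -2 = 20 mg, then discontinue cobimetinib.
- 40 mg start: -1 = 20 mg, then discontinue cobimetinib.

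Align Section 8.2.4: two cobimetinib reductions for a 60 mg start and one for a 40 mg start. The relative wording in Appendix 1 then works as it stands. The cost is one table and one sentence in an amendment, with no added patients or procedures.

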8.2.3 Dose modifications: Hydroxychloroquine

Allowable dose modifications for Hydroxychloroquine are described in Table 7.

The 4-aminoquinoline compounds are very rapidly and completely absorbed after ingestion. In accidental overdosage, or rarely with lower doses in hypersensitive patients, toxic symptoms may occur within 30 minutes. The symptoms of overdosage may include headache, drowsiness, visual disturbances, cardiovascular collapse, convulsions, hypokalemia, rhythm and conduction disorders, including QT prolongation, torsades de pointes, ventricular tachycardia and ventricular fibrillation, followed by sudden, potentially fatal respiratory and cardiac arrest. Treatment is symptomatic and must be prompt. Immediate gastric lavage until the stomach is completely emptied is indicated. After lavage, activated charcoal is introduced by the stomach tube within 30 minutes of ingestion of the drug may inhibit further intestinal absorption. To be effective, the dose of activated charcoal should be at least five times the estimated dose of hydroxychloroquine ingested.

Consideration should be given to administering diazepam parenterally since studies suggest that it may be beneficial in reversing chloroquine and hydroxychloroquine cardiotoxicity.

Respiratory support and shock management should be instituted as necessary.

Exchange transfusions are used to reduce the level of 4-aminoquinoline drug in the blood.

Columbia University Irving Medical Center
Herbert Irving Comprehensive Cancer Center
AAAS4165_Version Date: 07/07/2021

A patient who survives the acute phase and is asymptomatic should be closely observed for at least six hours. Fluids may be forced and sufficient ammonium chloride (8 g daily in divided doses for adults) may be administered for a few days to acidify the urine. This will promote urinary excretion in cases of both overdosage and sensitivity. However, caution must be exercised in patients with impaired renal function and/or metabolic acidosis.

Table 7. Hydroxychloroquine dose modification

| Dose Level | Hydroxychloroquine (mg) TDD |
|-------------------|---------------------------------------|
| -1 | 1000mg (400mg AM and 600mg PM orally) |
| -2 | 800mg (400mg BID orally) |
| -3 | 600mg (200mg AM and 400mg PM orally) |

